## 8.0 DATA SAFETY AND MONITORING

### 8.1 Data safety monitoring plan

All subject data will be collected by the University of Pittsburgh Cancer Institute's Protocol Office. All data will be secured in a password protected file with observance of all applicable HIPAA regulation. A data safety monitoring board will meet monthly to evaluate toxicity for this trial. Subjects/adverse events will be discussed at these monthly disease center meetings. Unexpected serious adverse events will be reported to the IRB and DSMC, and minutes of the monthly disease center meetings will be reviewed at the DSMC meetings.

#### 8.1.1 Subject Removal Criteria

1. Disease progression
2. Development of a serious medical illness
3. Evidence of dose-limiting toxicity
4. Voluntary withdrawal
5. Protocol violation
6. Discretion of the principal investigator
7. Development of grade 4 toxicity related to experimental therapeutic

### 8.2 Safety Reporting

#### 8.2.1 Adverse Event Characteristics

**CTCAE term (AE description) and grade:** The descriptions and grading scales found in the revised NCI Common Terminology Criteria for Adverse Events (CTCAE) version 4.0 will be utilized for AE reporting. All appropriate treatment areas will have access to a copy of the CTCAE version 4.0. A copy of the CTCAE version 4.0 can be downloaded from the CTEP web site (<http://ctep.cancer.gov>).

An AE is any untoward medical occurrence in a subject or clinical investigation subject administered a pharmaceutical product that does not necessarily have a causal relationship with this treatment. An AE can therefore be any unfavorable and unintended sign (including an abnormal laboratory finding), symptom, or disease temporally associated with the use of a medicinal (investigational) product, whether or not related to the medicinal (investigational) product.

It may include worsening or increase in severity of signs or symptoms of the illness, increase in frequency of signs and symptoms of an intermittent illness, or the appearance of a new manifestation/complication.

Exacerbation of a pre-existing illness should be considered when a subject requires new or additional concomitant drug or non-drug therapy for the treatment of that illness during the study. Lack of or insufficient clinical response, benefit, efficacy, or therapeutic effect should not be recorded as an adverse event. The investigator must make the distinction between exacerbation of pre-existing illness and lack of therapeutic efficacy.

In addition, abnormal objective test findings (e.g., electrocardiogram changes, abnormal

laboratory test results) that can result in a change in study drug dosage or in discontinuation of the drug, or require intervention or diagnostic evaluation to assess the risk to the subject, should also be recorded as adverse events. Clinically significant changes in physical examination findings should also be recorded as adverse events. For all adverse events, the investigator must pursue and obtain information adequate both to determine the outcome of the adverse event and to assess whether it meets the criteria for classification as a serious adverse event requiring immediate notification to UPCI or its designated representative.

*All observed or volunteered adverse events regardless of treatment group or suspected causal relationship to study drug will be recorded on the adverse event page(s) of the CRF. The investigator will record all adverse events in the CRF and assess each event as to severity and causal relationship to study drug.*

**‘Expectedness’:** AEs can be ‘Unexpected’ or ‘Expected’ for expedited reporting purposes only.

**Attribution** of the AE:

Definite – The AE *is clearly related* to the study treatment.

Probable – The AE *is likely related* to the study treatment.

Possible – The AE *may be related* to the study treatment.

Unlikely – The AE *is doubtfully related* to the study treatment.

Unrelated – The AE *is clearly NOT related* to the study treatment.

For all adverse events, sufficient information should be obtained by the investigator to determine the causality, (i.e., study drug or other illness). The investigator is required to assess causality and indicate that assessment on the CRF. Follow-up of the adverse event, after the date of therapy discontinuation, is required if the adverse event or its sequelae persist. Follow-up is required until the event or its sequelae resolve or stabilize at a level acceptable to the investigator. Adverse events that continue, or emerge within 30 days, after the subject’s discontinuation or completion of the study will be followed until the events resolve, are considered stable, or can be ascribed to causes other than study treatment.

All serious AE shall be reported meeting criteria for reporting can be found on the University of Pittsburgh Institutional Review Board’s website at <http://www.urb.pitt.edu>. In the event of such adverse event, the investigator must report the event(s) via phone within 24 hours and a written report filed within 24 hours to the Principal Investigator, or the UPCI’s Clinical Research Office.

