#### *5.3 On-Treatment assessment and post-treatment toxicity evaluation*

All subjects will be seen prior to delivery of each fraction of SBRT with toxicity evaluated by physical examination. Subsequently, subjects will be evaluated for toxicity 10-12 weeks later and then every 3 months until at least 2 years. Toxicities will be scored by the NCI CTC AE version 4.0. Also see Section 6.0.

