#### *6.4.5 Safety evaluation*

All patients will be monitored for potential treatment-related toxicity throughout treatment as detailed in the schema. Toxicity will be graded according to the CTCAE, which is further detailed in section 8.2.1. Acute toxicity is defined as toxicity occurring within 3 months of completion of SBRT. Late toxicity is defined as toxicity occurring greater than 3 months after treatment.

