### 7.3. Statistical Analyses

#### 7.3.1. Analysis Set

The data from all evaluable patients will be used in the analyses of survival, safety, tumor response, and health related QOL. Evaluable patients are those meeting all of the protocol inclusion/exclusion criteria and receiving at least one fraction of SBRT.

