#### 7.3.3 Analysis of Study Endpoints

Survival (LPFS, OS, TTP) will be estimated by the Kaplan-Meier method for all evaluable patients and the corresponding median survival times (with 95% confidence interval) reported. The 2-year LPFS will also be estimated along with its 95% confidence interval. The effect of variables listed in Section 7.3.2 will be explored with Cox regression models.

For the QOL data analysis, each item of the FACT-G will be individually assessed. The mean and standard deviation of the observed data will be summarized at each collection time and plotted against time, from baseline through the end of patient follow-up. Generalized linear models (such as cumulative logit models) for repeated measures will be used to explore if there are significant changes in HRQOL over time.

Using NCI Common Terminology Criteria for Adverse Events (CTCAE v4.0), the number of patients experiencing adverse events over their course of treatment will be characterized by type of adverse event and grade, by the time of onset in relation to the first day of therapy, and whether the event is clinically significant. Attribution of adverse events to treatment (unrelated, unlikely, possibly, probably, or definitely) will also be summarized for any serious adverse events (SAEs), CTCAE grade 3 or higher. The percentage of patients experiencing SAEs that are considered to be treatment-related (probable or definite) will be determined. The percentage of patients experiencing the acute and late toxicities associated with SBRT (as defined in Section 6.4) will also be estimated along with its 95% confidence interval.

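### The protocol does not say whether subjects removed from study stay on the 24-month toxicity schedule; if they do not, the crude late-toxicity percentage is biased downward

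*Combined protocol and SAP*

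**What the plan says.** **Definitions.** Section 6.4.5 splits toxicity at 3 months: "Acute toxicity is defined as toxicity occurring within 3 months of completion of SBRT", and "Late toxicity is defined as toxicity occurring greater than 3 months after treatment".

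**Schedule.** Section 5.3: "Subsequently, subjects will be evaluated for toxicity 10-12 weeks later and then every 3 months until at least 2 years". Section 6.2 likewise follows subjects for 24 months after treatment or until death. Neither section mentions subjects who have been removed.

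**Removal.** Section 8.1.1 lists seven grounds. The first is disease progression. Others are dose-limiting toxicity and "Development of grade 4 toxicity related to experimental therapeutic". The section does not say what is collected afterwards.

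**After leaving the study.** Section 8.2.1: "Adverse events that continue, or emerge within 30 days, after the subject’s discontinuation or completion of the study will be followed" until they resolve, stabilise or are attributed to another cause. The same section asks for every observed or volunteered adverse event to be recorded, with no time limit.

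**Analysis.** Section 7.3.1 counts as evaluable every eligible patient "receiving at least one fraction of SBRT", with no minimum follow-up. Section 7.3.3 estimates "The percentage of patients experiencing the acute and late toxicities associated with SBRT" with a 95% confidence interval. It gives no rule for patients without late follow-up and none for death.

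**The concern.** The 30-day window is shorter than the 3 months that must pass before a toxicity can be called late. SBRT is three fractions on alternate days, so most removals, and nearly all those for progression, will come after treatment has ended. Removal then reads naturally as leaving the study, and a site could reasonably stop toxicity visits and apply the 30-day sentence. Another site could keep the subject on the section 5.3 schedule. The text permits both.

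On the first practice, a removed subject has little or no observed late period but still counts in the denominator, in effect as free of late toxicity. The loss may also be informative, because two removal grounds are themselves toxicity. Late toxicity is a secondary objective (section 2.5), and section 3.3 gives reduced late effects as a reason for the fractionation, so an understated figure would bear on one of the trial's main arguments.

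**Working it through.** **The plan's own figure.** The plan states no late-toxicity rate, removal rate or onset pattern. Its one design figure, 94% power with 50 patients, reproduces: a simulated one-sample log-rank test with 2-year LPFS of 40% against 60%, 24 months of accrual plus 24 of follow-up and one-sided 0.05 gives 0.942. It does not depend on this point.

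**Who has no late window.** On the strict reading, observation ends at removal plus about 1 month. That falls short of month 3 only if removal comes before about month 2. A subject removed at the 10-12 week visit is covered to day 70 + 30 = 100 or 84 + 30 = 114, which is 9 to 23 days past a 3-month mark of about day 91.

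**Share of late toxicities captured.** Assumptions: removal is exponential with a proportion q removed by month 24; removal is independent of late toxicity; onset is uniform over months 3 to 24; nothing is captured after removal plus 1 month; death is ignored.

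- Removal rate per month: λ = −ln(1 − q)/24.
- An onset at month t is captured if removal is at t − 1 or later, with probability exp(−λ(t − 1)).
- Averaged over months 3 to 24: captured share = [exp(−2λ) − exp(−23λ)]/(21λ).
- Share of all patients with no late window: 1 − exp(−2λ).

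For q = 40%, which equals local progression alone if the 60% LPFS target is met: λ = 0.02128, and (0.9583 − 0.6129)/0.4470 = 0.773.

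The early-weighted columns let onset decay from month 3 on a 6-month scale.

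| Removed by 24 months (assumed) | Captured, uniform | True 20% reads | Captured, early-weighted | True 20% reads | No late window, of 50 |
|---|---|---|---|---|---|
| 20% | 89% | 17.8% | 94% | 18.7% | 0.9 |
| 40% | 77% | 15.5% | 86% | 17.2% | 2.1 |
| 60% | 64% | 12.7% | 77% | 15.3% | 3.7 |
| 80% | 47% | 9.4% | 64% | 12.8% | 6.3 |

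**Other true rates.** The 20% is an assumption. Section 1.3.1 reports 8% late grade 1-2 toxicity in 24 post-operative patients. With uniform onset and 20% to 80% removal this would read 8% × 0.892 = 7.1% to 8% × 0.469 = 3.8%. The SBRT background section cites 47% grade 2 or greater late toxicity after single-fraction treatment of intact tumours. That would read about 42% to 22%.

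**Against sampling error.** At a true 20% with 50 patients, the 95% half-width is about 1.96 × √(0.2 × 0.8/50) = 11 points. The uniform-onset shift runs from 20 − 17.8 = 2.2 points to 20 − 9.4 = 10.6 points: small at the low end, about as large as the half-width at the high end.

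**The case against.** The strongest reply is that the plan already provides for late follow-up. Sections 5.3 and 6.2 run to 24 months or death without exempting anyone. The 30-day sentence in section 8.2.1 is a duty to pursue certain events to resolution and does not bar recording others; the same section records every observed or volunteered event. The endpoints point the same way: progression is a removal ground, yet OS runs to death and distant disease is not an LPFS event, so follow-up after progression is needed anyway. This stands to the extent that a reader might infer that later events may not be collected, and the text does not say so. What remains is that no sentence settles the matter, and an event in a subject who is no longer seen is neither observed nor volunteered.

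A reader might also infer that discontinued patients cannot contribute a late toxicity at all. That is true only of removals before about month 2, which is 0.9 to 6.3 of 50 in the table. Later removals lose part of the late period.

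The size can also be challenged. At the 8% institutional rate with average risk, 3 to 8 early removals in 50 would lower the figure only to 7.5% to 6.7% (8% × 47/50 and 8% × 42/50). That is fair for early removals taken alone, but it leaves out the larger group removed later, mainly for progression.

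Finally, section 7.3.3 does not say that unobserved patients count as non-events. That is an inference, though it is what a percentage over all evaluable patients does unless a rule says otherwise.

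**Conclusion.** The point holds as an unresolved conflict between sections 5.3 and 6.2 on one side and 8.1.1 and 8.2.1 on the other, combined with a crude percentage over everyone treated. If removal ends toxicity visits, the late-toxicity percentage is biased downward. The direction follows from the design; the size rests on removal and onset assumptions that the documents do not supply. Over 20% to 80% removal by 2 years with uniform onset, a true 20% would read about 18% to 9%; with early-weighted onset, about 19% to 13%. If sites in fact keep removed subjects on the schedule, the bias largely disappears.

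A reader might go further and infer that the section 7.4 stopping rule would be missed at its 33% threshold. The documents do not support that. The rule pools acute and late toxicity of grade 3-5, so a patient removed for grade 4 toxicity already counts, and a late-only percentage cannot be set against that threshold.

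The primary endpoint, sample size and power are untouched. This is a worthwhile and inexpensive correction to a secondary safety endpoint.

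**What to change.** 1. **Sections 8.1.1 and 8.2.1.** Reconcile them with 5.3 and 6.2 by stating that any subject who received at least one fraction stays on the existing toxicity schedule to 24 months, death or withdrawal of consent to follow-up, whatever the reason for removal. Where visits are declined, allow toxicity to be collected by telephone or chart review. The removal grounds themselves are not at issue.
2. **Section 7.3.3.** Replace the crude late-toxicity percentage with a cumulative incidence to 24 months, with death as a competing event and censoring at the last toxicity assessment. With complete follow-up this equals the crude percentage, so it matters only where follow-up is cut short. Censoring cannot fully repair losses caused by toxicity itself, so the first change matters more.

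The cost is a sentence in each place, a few extra toxicity contacts on a schedule section 5.3 already sets, and a late-toxicity figure that may be slightly higher with a slightly wider interval.

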**APPENDIX A: Functional Assessment of Cancer Therapy - General (FACT-G)**

Below is a list of statements that other people with your illness have said are important. **Please circle or mark one number per line to indicate your response as it applies to the past 7 days.**

**PHYSICAL WELL-BEING**

		Not at all	A little bit	Some-what	Quite a bit	Very much
GP1	I have a lack of energy.....	0	1	2	3	4
GP2	I have nausea .....	0	1	2	3	4
GP3	Because of my physical condition, I have trouble meeting the needs of my family .....	0	1	2	3	4
GP4	I have pain .....	0	1	2	3	4
GP5	I am bothered by side effects of treatment .....	0	1	2	3	4
GP6	I feel ill .....	0	1	2	3	4
GP7	I am forced to spend time in bed .....	0	1	2	3	4

**SOCIAL/FAMILY WELL-BEING**

		Not at all	A little bit	Some-what	Quite a bit	Very much
GS1	I feel close to my friends .....	0	1	2	3	4
GS2	I get emotional support from my family .....	0	1	2	3	4
GS3	I get support from my friends.....	0	1	2	3	4
GS4	My family has accepted my illness .....	0	1	2	3	4
GS5	I am satisfied with family communication about my illness.....	0	1	2	3	4
GS6	I feel close to my partner (or the person who is my main support).....	0	1	2	3	4
Q1	Regardless of your current level of sexual activity, please answer the following question. If you prefer not to answer it, please mark this box  and go to the next section.					
GS7	I am satisfied with my sex life.....	0	1	2	3	4

Please circle or mark one number per line to indicate your response as it applies to the past 7 days.

**EMOTIONAL WELL-BEING**

		Not at all	A little bit	Some-what	Quite a bit	Very much
GE1	I feel sad .....	0	1	2	3	4
GE2	I am satisfied with how I am coping with my illness .....	0	1	2	3	4
GE3	I am losing hope in the fight against my illness .....	0	1	2	3	4
GE4	I feel nervous .....	0	1	2	3	4
GE5	I worry about dying .....	0	1	2	3	4
GE6	I worry that my condition will get worse .....	0	1	2	3	4

**FUNCTIONAL WELL-BEING**

		Not at all	A little bit	Some-what	Quite a bit	Very much
GF1	I am able to work (include work at home) .....	0	1	2	3	4
GF2	My work (include work at home) is fulfilling .....	0	1	2	3	4
GF3	I am able to enjoy life .....	0	1	2	3	4
GF4	I have accepted my illness .....	0	1	2	3	4
GF5	I am sleeping well .....	0	1	2	3	4
GF6	I am enjoying the things I usually do for fun .....	0	1	2	3	4
GF7	I am content with the quality of my life right now .....	0	1	2	3	4

## **APPENDIX B: Karnofsky Performance Scale**

100	Normal; no complaints; no evidence of disease
90	Able to carry on normal activity; minor signs or symptoms of disease
80	Normal activity with effort; some sign or symptoms of disease
70	Cares for self; unable to carry on normal activity or do active work
60	Requires occasional assistance, but is able to care for most personal needs
50	Requires considerable assistance and frequent medical care
40	Disabled; requires special care and assistance
30	Severely disabled; hospitalization is indicated, although death not imminent
20	Very sick; hospitalization necessary; active support treatment is necessary
10	Moribund; fatal processes progressing rapidly
0	Dead

## APPENDIX C: ECOG Performance Status

Grade	ECOG
0	Fully active, able to carry on all pre-disease performance without restriction
1	Restricted in physically strenuous activity but ambulatory and able to carry out work of a light or sedentary nature, e.g., light house work, office work
2	Ambulatory and capable of all selfcare but unable to carry out any work activities. Up and about more than 50% of waking hours
3	Capable of only limited selfcare, confined to bed or chair more than 50% of waking hours
4	Completely disabled. Cannot carry on any selfcare. Totally confined to bed or chair
5	Dead

## **APPENDIX D: Staging for Pancreas**

### **Primary Tumor (T)**

- TX Primary tumor cannot be assessed
- T0 No evidence of primary tumor
- Tis in situ carcinoma
- T1 Tumor limited to the pancreas 2 cm or less in greatest dimension
- T2 Tumor limited to the pancreas more than 2 cm in greatest dimension
- T3 Tumor extends beyond the pancreas but without involvement of the celiac axis or the superior mesenteric artery
- T4 Tumor involves the celiac axis or the superior mesenteric artery (unresectable primary tumor)

### **Regional Lymph Nodes (N)**

- NX Regional lymph nodes cannot be assessed
- N0 No regional lymph node metastasis
- N1 Regional lymph node metastasis

### **Distant Metastasis (M)**

- MX Presence of distant metastasis cannot be assessed
- M0 No distant metastasis
- M1 Distant metastasis

### **Stage Grouping**

Stage 0	Tis	N0	M0
Stage Ia	T1	N0	M0
Stage Ib	T2	N0	M0
Stage IIa	T3	N0	M0
Stage IIb	T1-3	N1	M0
Stage III	T4	Any N	M0
Stage IV	Any T	Any N	M1

From American Joint Committee on Cancer. *AJCC Cancer Staging Manual, 6th ed.* New York: Springer-Yearlab, 2010:157-164
